6.3.4 Safety Analysis

6.3.4.1 Adverse Events

An adverse event (AE) is any untoward medical occurrence in a patient participating in clinical research.

Ocular and systemic AEs will be collected by the investigator (or authorised assessor/delegate) at each visit. In case of appearance of a new clinically significant sign or symptom, it should be reported as an AE. In case of clinically significant worsening of a pre-existing sign or symptom, it should be reported as an AE.

Both ocular and systemic AEs will be reported during the investigation and will be coded using MedDRA Version 27.1. Summary tables will be created for TEAEs. Ocular and systemic TEAEs will be analysed separately on the basis System Organ Class (SOC), by treatment group and overall,

The summary tables will include the number of patients and the number of events, where applicable. Percentages will be based on the number of patients in the SAF. For summaries by SOC and Preferred Term (PT), a patient will be counted once at the SOC level and once at each PT level within the SOC level.

This document is confidential.

Statistical Analysis Plan

Sponsor: Laboratoires Théa; Clinical Investigational Plan No.: LT2769-004

Therefore, patients may only contribute once to each PT and once to each SOC level. The summaries presenting frequency of AEs by SOC and PT will be ordered by overall descending frequency of SOC and then, within a SOC, by overall descending frequency of PT.

All AEs will be assessed for the relationship of the AE to IMD. [REDACTED]

Summary tables that will be provided are:

- An overall summary of the number and percentage of patients experiencing at least one TEAE, serious TEAE, IMD-related TEAE, IMD-related serious TEAE, TEAE leading to premature IMD discontinuation – and separately for ocular and systemic AEs.
- Number and percentage of patients with TEAEs, by SOC, PT and severity – separately for ocular and systemic AEs.
- Number and percentage of patients with TEAEs, by SOC, PT and relationship to IMD – separately for ocular and systemic AEs.
- Number and percentage of patients experiencing at least one serious TEAE, as well as the number of serious TEAEs, by SOC, PT and relationship to IMD – separately for ocular and systemic.
- Number and percentage of patients experiencing at least one TEAE leading to premature IMD discontinuation, by SOC and PT – separately for ocular and systemic AEs.
- Number and percentage of patients experiencing at least one serious TEAE, as well as the number of serious TEAEs, by SOC and PT – ocular and systemic AEs together.
- Number and percentage of patients experiencing at least one non-serious TEAE, as well as the number of non-serious TEAEs, by SOC and PT – ocular and systemic AEs.
- Number and percentage of patients experiencing at least one non-serious TEAE with PT occurring for at least 5% of the patients, as well as the number of non-serious TEAEs, by SOC and PT – ocular and systemic AEs.

Individual data listings will include all collected information, i.e. brief description of the event (diagnosis, localisation etc.), date and time of onset, time to AE occurrence, duration (days), intensity of symptoms (severity), treatment required, relationship with IMD and CIP procedure, action taken with the IMD, outcome, date and time of resolution and whether the event is classified as serious. [REDACTED]

Individual data listings that will be provided are:

[figure not shown]
- TEAEs – separately the ocular and systemic
- Non-TEAEs
- STEAEs
- TEAE leading to premature IMD discontinuation

This document is confidential.

Statistical Analysis Plan

Sponsor: Laboratoires Théa; Clinical Investigational Plan No.: LT2769-004

All aforementioned analyses will be performed in the SAF set, apart from the non-TEAEs listing which will be created in the Enrolled set.

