6.3.8 Number of Patients Required to be Randomised in the Clinical Investigation

It is planned to randomise 74 patients in order to have 68 evaluable patients (34 per group) for the FAS analysis.

Evaluable patients will be defined as randomised patients having received at least one dose of IMD and with at least one performance endpoint post-randomisation visit.

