7.2.2 Safety Analyses

Safety endpoints will be analysed on the Safety set.

Ocular and systemic adverse events (AEs)

Ocular and systemic AE reported during the investigation will be coded using the Medical Dictionary for Regulatory Activities (MedDRA dictionary).

Summary tables will be performed on Treatment-Emergent AEs (TEAEs).

Ocular and systemic TEAEs will be analysed separately on the basis of the localisation and System Organ Class (SOC).

TEAEs are AEs that occurred after the first IMP instillation. For the AEs that occurred the day of the first IMP instillation, a question on the eCRF will establish the timing compared to the first instillation.

Separate descriptions of ocular (for both, study and contralateral eye together) and systemic TEAEs will be performed by treatment group:

- An overall summary of the number and percentage of patients experiencing at least one AE, SAE, IMD-related AE, IMD-related SAE and AE leading to premature investigation IMD discontinuation.
- Number and percentage of patients experiencing at least one AE, as well as the number of AEs, by SOC and Preferred Term (PT). The summaries will be performed for AEs leading to premature IMD discontinuation.
- Number and percentage of patients with AEs, by SOC, PT and severity.

- Number and percentage of patients with AEs, by SOC, PT and relationship to IMD.

[figure not shown]
Documented list of individual data concerning TEAEs will be performed.

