14.5 RECORDING AES

AEs recording and reporting will extend from signing of informed consent until the final visit. If the investigator is aware of an AE occurring within one month after final investigation visit and that he/she considers there is a causal relationship with the IMD, the AE should be recorded in the e-CRF. An incident form must also be recorded by the unmasked collaborator.

The investigator shall:

- a) Record all AEs, regardless of the relationship to IMD and seriousness, in the e-CRF together with an assessment. For each AE, a corresponding incident form must also be recorded by the masked collaborator.
- b) Supply the Sponsor, upon Sponsor's request, with any additional information related to the safety reporting of a particular event.

All AE reports should contain: a brief description of the event (diagnosis, localisation ...), date and time of onset (if needed), duration (hours or days), intensity of symptoms (severity), treatment required, relationship with IMD and CIP procedure, action taken with the IMD, outcome, date and time of resolution and whether the event is classified as serious.

If there is a worsening of a medical condition that was present before starting the clinical investigation, this should be considered as a new AE and a complete evaluation should be recorded.

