3.2.3 Safety Endpoints

The safety endpoints are:

- Treatment-Emergent Adverse Event (TEAE) by System Organ Class (SOC) and Preferred Term (PT) (separately for ocular and systemic TEAE).

This document is confidential.

Statistical Analysis Plan

Sponsor: Laboratoires Théa; Clinical Investigational Plan No.: LT2769-004

4. Study Design

This is a 5-week, international, multicentre, randomised, investigator-masked, 2 parallel groups (T2769 versus Hylo-Forte®) investigation. The clinical investigation design is confirmatory.

- Multicentre

The investigation will be performed in different sites in European Union (EU).

- Randomised

Eligible patients will be randomised on a 1:1 basis to T2769 or Hylo-Forte® respectively at the Randomisation Visit on Day 1 (Visit #2 - D1).

- Run-in period

Patients meeting the screening criteria will undergo a 7-10-days run-in period. During this period, all patients will substitute their current dry eye treatment with Hydrabak®, ophthalmic solution containing NaCl 0.9%. This period will allow to verify signs and symptoms of DES, and to facilitate the washout from the ocular surface of previous artificial tears treatment. Patients will instil 1 drop in each eye, from 3 to 6 times daily.

- Investigator-masked

A double-masked investigation design is not possible due to different commercial packaging between T2769 – Hylo-Forte®. However, the identity of the Investigational Medical Device (IMD) given to each patient will not be known for the masked investigator who is independently in charge of the ophthalmic examination. To this aim, the masked investigator will differ from the person who will record the used/unused IMDs. The masked investigator should not receive the returned IMDs from the patients and returned IMD must be stored in a different place from the IMD that have not yet been dispensed. Patients will also be trained to not report any information that could lead to unblinding in the diary and to the masked investigator.

- Exposure to the IMD

IMD will be administered by the patient every day from D1 until Visit 4 (included), one drop in each eye 3 to 6 times daily into the lower conjunctival sac of each eye.

No IMD instillation must be done at least 2 hours before Visit#3 and 4. However, the first instillation can be done any time after the patient has completed the randomisation visit.

There will be two treatment groups:

- T2769 (test medical device)
- Hylo-Forte® (comparative medical device)

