6.2.6 Ocular and Systemic Medical and Surgical History (other than dry eye)

All ocular and systemic medical and surgical history (other than dry eye) will be coded using Medical Dictionary for Regulatory Activities (MedDRA) Version 27.1.

The history will be assumed as ocular or systemic, [REDACTED]. In addition, category will be validated based on the SOC. [REDACTED]

Medical and surgical history will be summarized separately for ocular and systemic history by the number and percent of patients within each SOC and PT in the FAS, PP and SAF sets [REDACTED] [REDACTED]. Conditions that are reported more than once for a given SOC and PT will be counted only once per patient on the PT level for each SOC. Medical and surgical history will be sorted by descending overall frequency, by SOC and PT in the summary table.

All above data will also be listed separately for ocular and systemic history, sorted by patient number, onset date, SOC, and PT in the SAF set.

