6.4 Interim Analysis

Not applicable. No interim analysis is planned for this investigation.

This document is confidential.

Statistical Analysis Plan

Sponsor: Laboratoires Théa; Clinical Investigational Plan No.: LT2769-004

This document is confidential.

SAP text and shells Version: 2.0 07-FEB-2025

Page 28 of 46

Statistical Analysis Plan

Sponsor: Laboratoires Théa; Clinical Investigational Plan No.: LT2769-004

7. Tables, Figures and Listings

[figure not shown]
Mock tables, listings, and figures will be provided in an external document that accompanies this SAP.

This document is confidential.

Statistical Analysis Plan

Sponsor: Laboratoires Théa; Clinical Investigational Plan No.: LT2769-004

[figure not shown]
This document is confidential.

SAP text and shells Version: 2.0 07-FEB-2025

Page 30 of 46

Statistical Analysis Plan

Sponsor: Laboratoires Théa; Clinical Investigational Plan No.: LT2769-004

This document is confidential.

[figure not shown]
Statistical Analysis Plan

Sponsor: Laboratoires Théa; Clinical Investigational Plan No.: LT2769-004

This document is confidential.

Statistical Analysis Plan

[figure not shown]
Sponsor: Laboratoires Théa; Clinical Investigational Plan No.: LT2769-004

This document is confidential.

Statistical Analysis Plan

[figure not shown]
Sponsor: Laboratoires Théa; Clinical Investigational Plan No.: LT2769-004

This document is confidential.

Statistical Analysis Plan

Sponsor: Laboratoires Théa; Clinical Investigational Plan No.: LT2769-004

[figure not shown]
This document is confidential.

SAP text and shells Version: 2.0 07-FEB-2025

Page 35 of 46

Statistical Analysis Plan

Sponsor: Laboratoires Théa; Clinical Investigational Plan No.: LT2769-004

[figure not shown]

This document is confidential.

[figure not shown]
SAP text and shells Version: 2.0 07-FEB-2025

Page 36 of 46

[figure not shown]
11. Deviations of the SAP from the CIP

[figure not shown]
[REDACTED] deviations from the CIP are the following:

- In the CIP it was stated that the summary tables would include the 95% CI for the mean/median (continuous variables) and the 95% CI of the percentages (categorical variables). However, this was removed from the SAP as it was found to not add any extra value while was increasing the complexity of the outputs.

- For Adverse event reporting, more summary tables and details on listings to be provided are outlined in the SAP section 6.3.4.1 in comparison with the CIP.

Statistical Analysis Plan

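### Does the SAP drop localisation when it separates ocular from systemic adverse events?

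*SAP*

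**What the plan says.** CIP 7.2.2 gives two criteria: "Ocular and systemic TEAEs will be analysed separately on the basis of the localisation and System Organ Class (SOC"). The matching sentence in SAP 6.3.4.1 shows one: "Ocular and systemic TEAEs will be analysed separately on the basis System Organ Class (SOC), by treatment group and overall".

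The split feeds a named endpoint. CIP 6.1.2.8 and SAP 3.2.3 both list TEAEs by SOC and preferred term, "separately for ocular and systemic TEAE".

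Localisation is collected and reported. CIP 14.5 requires each adverse event report to contain "a brief description of the event (diagnosis, localisation" among other items, and the SAP 6.3.4.1 listings include the "brief description of the event (diagnosis, localisation etc".

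Two other places in the SAP bear on the point:
- Section 6.2.6 splits medical history into ocular and systemic by a criterion that is blacked out, then adds: "In addition, category will be validated based on the SOC".
- Section 11 lists departures from the CIP. Its adverse event item says only that "more summary tables and details on listings to be provided are outlined in the SAP section 6.3.4.1 in comparison with the CIP".

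**The concern.** The two sentences are nearly identical except that the reference to localisation is missing from the SAP. CIP 7.15 requires changes from the planned analyses to be described and justified in the SAP and the final report, and the readable part of SAP section 11 mentions no change to this criterion. It therefore looks like an undeclared switch from two criteria to one.

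If SOC were the only criterion, an event in the treated eye whose term was coded to another class would be tabulated as systemic. The product is an eye drop for which CIP 5.1 records a claim of good tolerance on the ocular surface. A rule that moved ocular events into the systemic tables would lower the reported ocular rate and raise the systemic one, in the only safety endpoint legible in both documents. The history rule in SAP 6.2.6, where SOC serves as a check on a category already assigned, makes the contrast sharper.

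**Working it through.** The plan gives no figure on this point, so the check is mainly a comparison of texts, followed by one calculation of scale.

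**1. The passages side by side**

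| Place | Basis for the ocular/systemic split | State of the text |
|---|---|---|
| CIP 7.2.2 (TEAEs) | Localisation and SOC | Complete |
| SAP 6.3.4.1 (TEAEs) | SOC in the legible words | A word is missing after *basis*; the sentence ends on a comma after *overall* |
| SAP 6.2.6 (history) | A first criterion, then SOC as validation | First criterion blacked out |
| SAP 11 (deviations) | Adverse event item covers tables and listings | Opening words blacked out |

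The gap in the SAP sentence falls exactly where the CIP mentions localisation. The SAP also loses text elsewhere without a redaction mark: in 6.3.1 one fragment begins in mid-word and another lacks its subject. A lost phrase is therefore a live explanation, as is a drafting slip. Neither is a decision to abandon the criterion.

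**2. What an SOC-only reading implies**

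SAP 3.2.3 and several tables in 6.3.4.1 report ocular TEAEs by SOC and preferred term. If ocular meant membership of a single eye class, the SOC layer in those ocular tables would carry no information. A shared table template could explain this, so it is only weak evidence, but it points away from an SOC-only rule.

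**3. What misfiling would require**

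Three things must hold together:
- SOC is the only criterion applied.
- Some eye events are coded outside the eye class.
- For a patient-level rate to move, all of that patient's ocular events are so coded.

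The first is not shown by the text. On the second, neither document says which terms would be affected. CIP 14.9 lists the foreseeable effects: eye irritation, redness, burning, stinging, foreign body sensation and blurred vision. Nothing in the documents indicates that any of these would be coded elsewhere.

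**4. Scale**

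Inputs: 74 patients randomised (CIP 6.3.8), allocation 1:1 (CIP 6.1.2.1). Assumption: all randomised patients enter the safety set, so the arm size is 74/2 = 37.

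Shift in an arm's ocular TEAE rate if *k* patients are misfiled = *k*/37:
- *k* = 1: 1/37 = 2.7 percentage points
- *k* = 2: 2/37 = 5.4 percentage points
- *k* = 3: 3/37 = 8.1 percentage points

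The values of *k* are illustrative; the documents offer no basis for choosing one.

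**5. What would be unaffected or recoverable**

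The primary analysis and the total number of patients with a TEAE do not use the split. SAP 6.3.4.1 also tabulates serious TEAEs with ocular and systemic events together. Every term stays visible by SOC and preferred term, and localisation is listed for each event, so a reader could identify a misplaced event.

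**The case for a change.** The strongest case for acting is that the words differ, the difference is not declared in any legible text, and the remedy is cheap. Localisation is already recorded, one sentence in SAP 6.3.4.1 would settle the rule, and CIP section 10 provides for a blind data review meeting before database lock at which disagreements could be settled. In a confirmatory trial of an eye drop, the definition of an ocular event should not be left to inference.

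Part of this stands. The legible SAP text names one criterion where the CIP names two, and neither document says which prevails when localisation and SOC disagree. A sponsor holding the unredacted SAP could usefully confirm the wording.

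The rest does not carry. The alleged inconsistency with SAP 6.2.6 rests on a criterion nobody outside the sponsor can read; if anything, that section shows this SAP pairing SOC with something else for the same kind of split. The deviation list cannot be treated as complete when part of it is hidden. Which eye events would be coded outside the eye class depends on knowledge of the coding dictionary that the documents do not supply. Nor would restoring the CIP phrase resolve conflicts: the CIP joins the two criteria with *and* and gives no tie-break. A rule under which either criterion suffices would be a new choice, beyond anything the CIP says.

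**Conclusion.** No change to the plan is called for. What can be shown is a mismatch between a complete CIP sentence and a damaged SAP sentence, which is not enough to conclude that localisation was dropped. If the words really are absent from the full SAP, the gap is one that analysts fill sensibly: the CIP supplies the criterion, CIP 14.5 supplies the data, and CIP 7.15 would require any real departure to be described and justified.

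The possible effect is limited to the descriptive ocular and systemic tables and the listings divided in the same way. It would be 2.7 percentage points in an arm's ocular TEAE rate for each patient misfiled, assuming 37 per arm in the safety set, with the number of such patients unknown and possibly zero. The conclusion rests on treating lost or blacked-out text as unknown, and on the fact that no safety test legible in either document depends on the split. It would change if the full SAP were seen to define ocular TEAEs by SOC only and to disregard recorded localisation.

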6.4 Interim Analysis

Not applicable. No interim analysis is planned for this investigation.

This document is confidential.

Statistical Analysis Plan

Sponsor: Laboratoires Théa; Clinical Investigational Plan No.: LT2769-004

This document is confidential.

SAP text and shells Version: 2.0 07-FEB-2025

Page 28 of 46

Statistical Analysis Plan

Sponsor: Laboratoires Théa; Clinical Investigational Plan No.: LT2769-004

7. Tables, Figures and Listings

[figure not shown]
Mock tables, listings, and figures will be provided in an external document that accompanies this SAP.

This document is confidential.

Statistical Analysis Plan

Sponsor: Laboratoires Théa; Clinical Investigational Plan No.: LT2769-004

[figure not shown]
This document is confidential.

SAP text and shells Version: 2.0 07-FEB-2025

Page 30 of 46

Statistical Analysis Plan

Sponsor: Laboratoires Théa; Clinical Investigational Plan No.: LT2769-004

This document is confidential.

[figure not shown]
Statistical Analysis Plan

Sponsor: Laboratoires Théa; Clinical Investigational Plan No.: LT2769-004

This document is confidential.

Statistical Analysis Plan

[figure not shown]
Sponsor: Laboratoires Théa; Clinical Investigational Plan No.: LT2769-004

This document is confidential.

Statistical Analysis Plan

[figure not shown]
Sponsor: Laboratoires Théa; Clinical Investigational Plan No.: LT2769-004

This document is confidential.

Statistical Analysis Plan

Sponsor: Laboratoires Théa; Clinical Investigational Plan No.: LT2769-004

[figure not shown]
This document is confidential.

SAP text and shells Version: 2.0 07-FEB-2025

Page 35 of 46

Statistical Analysis Plan

Sponsor: Laboratoires Théa; Clinical Investigational Plan No.: LT2769-004

[figure not shown]

This document is confidential.

[figure not shown]
SAP text and shells Version: 2.0 07-FEB-2025

Page 36 of 46

[figure not shown]
11. Deviations of the SAP from the CIP

[figure not shown]
[REDACTED] deviations from the CIP are the following:

- In the CIP it was stated that the summary tables would include the 95% CI for the mean/median (continuous variables) and the 95% CI of the percentages (categorical variables). However, this was removed from the SAP as it was found to not add any extra value while was increasing the complexity of the outputs.

- For Adverse event reporting, more summary tables and details on listings to be provided are outlined in the SAP section 6.3.4.1 in comparison with the CIP.

Statistical Analysis Plan

Sponsor: Laboratoires Théa; Clinical Investigational Plan No.: LT2769-004

This document is confidential.

[figure not shown]
Statistical Analysis Plan

Sponsor: Laboratoires Théa; Clinical Investigational Plan No.: LT2769-004

This document is confidential.

Statistical Analysis Plan

[figure not shown]
Sponsor: Laboratoires Théa; Clinical Investigational Plan No.: LT2769-004

This document is confidential.

Statistical Analysis Plan

[figure not shown]
Sponsor: Laboratoires Théa; Clinical Investigational Plan No.: LT2769-004

This document is confidential.

Statistical Analysis Plan

Sponsor: Laboratoires Théa; Clinical Investigational Plan No.: LT2769-004

This document is confidential.

SAP text and shells Version: 2.0 07-FEB-2025

Page 42 of 46

Statistical Analysis Plan

Sponsor: Laboratoires Théa; Clinical Investigational Plan No.: LT2769-004

This document is confidential.

[figure not shown]
Statistical Analysis Plan

Sponsor: Laboratoires Théa; Clinical Investigational Plan No.: LT2769-004

This document is confidential.

Statistical Analysis Plan

[figure not shown]
Sponsor: Laboratoires Théa; Clinical Investigational Plan No.: LT2769-004

This document is confidential.

Statistical Analysis Plan

Sponsor: Laboratoires Théa; Clinical Investigational Plan No.: LT2769-004

This document is confidential.
